**Data Acquisition:** Rectal temperature, skin temperature, local sweat rate, and heart rate were sampled at 250 Hz (Biopac MP150, Santa Barbara, CA) and converted into 1-minute averages for data analysis. Core temperature measured via the telemetric pill (both ingested and as a suppository) was sampled every 30 seconds, and blood pressure was measured every 15 minutes during heat exposures.

**Statistical Analyses:** A power calculation was performed to detect a 0.5°C difference in the increase in core temperature between groups, with a standard deviation of that increase being 0.5°C. Based upon these estimates, and with an alpha of 0.05, 20 participants (10 participants per age group) would provide power of >0.80 to detect differences between age groups in the change in core temperature (power analyses from: NCSS PASS 2019). However, we enrolled 40 participants (20 participants per age group, with each age group comprising 10 males and 10 females) to account for possible attrition/missing data and to increase the capability to detect differences in other outcome variables that may have a greater degree of variability than core temperature. Due to technical difficulties, we were unable to obtain some measurements (e.g., skin temperature, local sweat rate, blood pressure, and limb blood flow) at either baseline or at the end of the extreme heat exposures in some participants. Similarly, we were unable to obtain metabolic heat production data in one young and one older participant. These missing data were excluded from final analyses, and the number of participants included for each variable is indicated in text, tables, and figures where appropriate. Before analyses, data were assessed to confirm that they met model assumptions (i.e., normality, equality of variance). Within each extreme heat simulation, we analyzed data using linear mixed effect models with main effects of time (within factor) and group (between factor; older vs young) or unpaired t-tests (two-tailed), as appropriate. Statistical analyses were performed in R studio (Version 2022.07.1), and graphs were generated using GraphPad Prism 9.4 (GraphPad Software Inc., La Jolla, CA, USA). Data in text, tables, and figures are presented as means  $\pm$  standard deviations. Statistical significance was set *a priori* to  $p < 0.05$ .

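### The power statement does not follow from its own inputs: 10 per age group give power of about 0.56, not above 0.80, and 0.80 needs 17 per group

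*Combined protocol and SAP*

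**What the plan says.** The whole sample-size argument is in the Statistical Analyses section of the combined protocol and SAP. The calculation was made "to detect a 0.5°C difference in the increase in core temperature between groups, with a standard deviation of that increase being 0.5°C", and "with an alpha of 0.05". From this the section concludes that "20 participants (10 participants per age group) would provide power of >0.80 to detect differences between age groups in the change in core temperature", and it cites a commercial power package.

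It then reports that 40 people were enrolled, 20 per age group. The reason given for going beyond 20 in total is "to account for possible attrition/missing data and to increase the capability to detect differences in other outcome variables", the latter being outcomes that may vary more than core temperature.

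The power sentence names neither the test nor its sidedness. The same section describes the analysis, within each heat simulation, as linear mixed models with time and group or "unpaired t-tests (two-tailed), as appropriate".

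**The concern.** Every input needed to check the claim is printed: difference, standard deviation, alpha and group size. The standard deviation is said to be that of the increase itself, so the difference is exactly one standard deviation. Ten per group is well short of what a two-group comparison usually needs to detect one standard deviation with 80% power.

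Two things depend on the figure. The first is the stated basis for the sample size, which a reader should be able to reproduce and which others may reuse for a similar two-group study. The second is the margin that the plan claims by doubling the sample. If 10 per group were enough, half of each group could be lost before power for core temperature fell below 0.80. If it is not enough, the margin is much smaller. This matters because the section itself reports that some measurements could not be obtained in some participants.

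**Working it through.** **Inputs, all from the Statistical Analyses section**

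- Difference in the increase: 0.5°C.
- Standard deviation of the increase: 0.5°C, so d = 0.5 / 0.5 = 1.0.
- Alpha: 0.05. Two-sided is taken from the description of the analysis; one-sided is also tried because the power sentence is silent.
- Group sizes: 10 per group in the calculation, 20 per group enrolled. Older and young participants are independent groups.

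**Formula.** For a two-sample t-test with n per group, df = 2n − 2 and the noncentrality is λ = d·√(n/2). Power is the probability that a noncentral t with these parameters falls beyond the critical value of the central t.

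**Attempt to reproduce the plan's figure (n = 10).** df = 18 and λ = 1.0 × √5 = 2.236.

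- Two-sided: critical t = 2.101, power = **0.562**.
- One-sided: critical t = 1.734, power = **0.694**.
- The normal approximation, which is optimistic at this size, gives 0.609 two-sided and 0.723 one-sided.

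None of these reaches 0.80.

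**Sample size that the inputs require**

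| n per group | Power, two-sided | Power, one-sided |
|---|---|---|
| 10 | 0.562 | 0.694 |
| 13 | 0.687 | 0.797 |
| 14 | 0.721 | 0.824 |
| 16 | 0.781 | 0.868 |
| 17 | 0.807 | 0.887 |
| 20 | 0.869 | 0.928 |

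The smallest n for 0.80 is 17 per group (34 in total) two-sided and 14 per group one-sided. A simulation with 400,000 trials per setting, two-sided, gives 0.561 at 10, 0.807 at 17 and 0.869 at 20.

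**What would make 10 per group give 0.80, two-sided.** The required d is 1.325. That means either a standard deviation of 0.5 / 1.325 = 0.377°C or a difference of 1.325 × 0.5 = 0.66°C. Neither is in the documents.

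**Other readings tried**

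- *0.5°C as the standard deviation of a single temperature.* The standard deviation of the change is then 0.5·√(2(1 − r)), and 0.377°C needs a pre-post correlation of r = 1 − (0.377/0.5)²/2 ≈ 0.72. No correlation is given, and the text says "with a standard deviation of that increase being 0.5°C".
- *Mean of the two heat exposures.* With zero within-person correlation between exposures power is 0.848; with a correlation of 0.25 it is 0.763. The plan analyses each exposure separately.
- *One-sample or paired t-test, n = 10, d = 1.0.* df = 9 and λ = √10 = 3.162, giving power 0.803. This matches the printed claim, but that test does not compare two independent age groups.

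**Margin at the enrolled size (d = 1.0, two-sided).** The losses here are hypothetical.

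- Equal loss of 3 per group: 0.807. Equal loss of 4 per group: 0.781.
- Loss in one group only, λ = d/√(1/n₁ + 1/n₂): 20 v 16 gives 0.825, 20 v 15 gives 0.811, 20 v 14 gives 0.795.
- Smallest standardised difference with 0.80 power at 20 per group: 0.909. For a 0.5°C difference this allows a standard deviation up to 0.5 / 0.909 = 0.55°C.

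**The case against.** The strongest reply is that nothing in the completed study turns on the sentence. The document is written after enrolment, 20 per group were recruited, and at that size core temperature has power 0.869 on the stated inputs. No missing core temperature data are reported. The only loss given as a number is that "we were unable to obtain metabolic heat production data in one young and one older participant"; the other gaps named are in skin temperature, sweat rate, blood pressure and limb blood flow. The plan gives no attrition rate and never states a margin of 10 per group: that comes from comparing its two sample sizes. All of this is correct, and it limits the consequence.

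A second reply is that the two-tailed unpaired test is named for the analysis, not for the power run, so the procedure actually used is unknown. This also stands, but it does not rescue the figure. The one-sided test fails too, and the claim is expressly about a difference between age groups in a change whose standard deviation is supplied. A mixed model does not add power to that comparison beyond what the stated standard deviation already contains, unless further assumptions are made that the plan does not state.

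What remains is a printed power that its own printed inputs do not deliver.

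**Conclusion.** The concern holds. With a 0.5°C difference, a standard deviation of the increase of 0.5°C, alpha 0.05 and two independent groups of 10, power is 0.56 two-sided (0.69 one-sided), not above 0.80. The two-sided shortfall is about 24 percentage points (0.80 − 0.562 = 0.238), too large for rounding or a choice of approximation. The size needed for 0.80 is 17 per group two-sided, and nothing elsewhere in the document corrects the statement.

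The conclusion assumes a comparison of two independent means with equal variances, and that the standard deviation is what the text says it is. Whether the error lies in the power, the standard deviation, the sidedness or the choice of test cannot be told without the software output. The match with a one-sample or paired calculation is a lead, not a finding.

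The effect on the study is limited. Core temperature is adequately powered as enrolled (0.87), and the margin over the required size is 3 per group (20 − 17). No target difference or standard deviation is given for other outcomes, so nothing follows about their power, except that any standardised difference below about 0.91 has less than 0.80 power at 20 per group. This should be fixed because the stated basis for the sample size is wrong as written and the correction is nearly free.

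**What to change.** Retrieve the original power output and check the procedure, the sidedness and the meaning of the standard deviation entered. Check first whether a one-sample or paired procedure was run.

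- If the inputs were those printed, remove the claim for 10 per group and put in its place, labelled as a recalculation: *With a 0.5°C difference, a standard deviation of the increase of 0.5°C and two-sided alpha 0.05, 17 per group (34 in total) are needed for 0.80 power; the 20 per group enrolled give 0.87.* The reason given for enrolling 40 should then be read against 34, not 20.
- If the run used other inputs, print them (test, sidedness, definition and value of the standard deviation, any assumed correlation), so that the stated power can be reproduced for a comparison of two independent groups.

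The cost is one look at a stored output and one or two sentences. Participants, tests and analyses are unaffected, because the 20 per group enrolled exceed the recalculated 17.

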Study Protocol and Statistical Analysis Plan

Heat Waves in the Elderly: Reducing Thermal and Cardiovascular Consequences

NCT04538144

August 23rd, 2024

**Experimental Protocol:** All experimental trials began between 8:00 and 10:00 to avoid diurnal variations. Before experimental trials, participants were instructed to eat a light breakfast (without caffeinated beverages) on the morning of testing. Alcoholic beverages and aerobic/resistance exercise were prohibited 24 hours before testing. Upon arrival, participants provided a urine sample and weighed themselves nude. A euhydrated state before each trial was confirmed by a urine specific gravity value  $\leq 1.020$  (Atago Inc., Bellevue, WA). If urine specific gravity was between 1.020 and 1.024, participants ingested 500 mL of water before testing. If their urine specific gravity was  $\geq 1.025$ , the trial was rescheduled to a later date. Participants rested in a temperate environment ( $\sim 22^{\circ}\text{C}$  and 40% humidity) for at least one hour while baseline measurements (e.g., heart rate, blood pressure, forearm blood flow, etc.) were performed. Following baseline measurements, participants entered the environmental chamber set to one of the following two extreme heat simulations: 1) DRY ( $47^{\circ}\text{C}$  and 15% humidity; reflective of the 2018 Los Angeles heatwave) and 2) HUMID ( $41^{\circ}\text{C}$  and 40% humidity; reflective of the 1995 Chicago heatwave). The duration of each exposure was 3 hours, which represents the approximate duration of peak environmental temperatures during a heatwave (4, 31). Before instrumentation, participants' body mass was measured using a precision balance scale with  $\pm 10$  g accuracy (Mettler Toledo, OH). After a brief period ( $\sim 5$ -minutes) of instrumentation, participants were seated in a semi-recumbent position on a chair with a breathable fabric thereby reducing impediments for thermal exchange from the regions in contact with the chair. To reduce the influence of clothing on thermoregulatory responses, participants wore athletic shorts (males) or athletic shorts and a sports bra (females). To decrease the effect of dehydration, participants consumed 3 mL/kg body mass of tap temperature water ( $14$ - $16^{\circ}\text{C}$ ) every hour during the extreme heat simulation. This level of fluid ingestion was based on pilot data and was selected to maintain hydration to a level that would not compromise thermoregulatory, perceptual, or cardiovascular responses during heat exposure (16, 54, 55). Tap water temperature was used to mimic the water available to individuals during an actual heatwave. Following the extreme heat simulation,

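### Sex is balanced 10/10 within each age group but absent from the analysis, so the age comparison is conservative for any outcome where sex affects the quantity tested

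*Combined protocol and SAP*

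**What the plan says.** The Statistical Analyses section reports 40 enrolled participants, 20 per age group, "with each age group comprising 10 males and 10 females". Sex is not called a stratification factor, but an exact 10/10 split in both groups implies a quota.

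The same section gives the analysis within each heat simulation: "linear mixed effect models with main effects of time (within factor) and group (between factor; older vs young"), or "unpaired t-tests (two-tailed), as appropriate". Sex is not named as a factor, covariate, interaction or subgroup, and no reason for omitting it is given. The random-effects structure of the mixed models is not spelled out.

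The power calculation was made "to detect a 0.5°C difference in the increase in core temperature between groups", "with a standard deviation of that increase being 0.5°C", "with an alpha of 0.05". The text does not say whether that SD is within sex or pooled over the sexes. Missing measurements are left out variable by variable.

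Outside the analysis text, sex appears in the Experimental Protocol section on clothing: "participants wore athletic shorts (males) or athletic shorts and a sports bra (females").

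**The concern.** When a factor is balanced across the groups by design, it cannot contribute to the difference between group means. A test that ignores the factor still counts its variance as noise. The estimate is right but the standard error is larger than the true sampling error, so p-values are too large and confidence intervals too wide. This happens only if sex affects the quantity tested: the change over time for a change contrast, or the level for a single-timepoint or group-main-effect test.

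What is at stake is sensitivity. The sample was doubled partly to help with outcomes more variable than core temperature, and a missed age difference in one of them could be read as no difference.

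A second route is possible. If exclusions leave different male-to-female ratios in the two age groups, part of any sex difference enters the unadjusted age contrast.

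**Working it through.** **Inputs from the Statistical Analyses section.** Difference 0.5°C, SD of the change 0.5°C, alpha 0.05, 20 per age group, 10 males and 10 females in each. Two-sided testing is stated for the t-tests and assumed for power.

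**Assumed.** R², the share of within-group variance due to sex, is not in the documents and is varied. The sex effect is taken as equal in both age groups.

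**The plan's own figure.** The text says "20 participants (10 participants per age group) would provide power of >0.80". A two-sided two-sample t-test with 10 per group and a standardised difference of 0.5/0.5 = 1 has power 0.56 (one-sided 0.69), so the figure does not reproduce for two independent groups. That is a separate matter. At the enrolled 20 per group, two-sided power is 0.869, which is the baseline here.

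**Sex difference implied by R².** With a 10/10 split and a male-female difference δ, the sex variance within an age group is (δ/2)². Hence R² = (δ/2)²/SD² and δ = 2 × SD × √R². With SD 0.5°C, δ = √R² in °C; for example √0.10 = 0.32°C.

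**Standard error.**
- Without sex: 0.5 × √(2/20) = 0.158°C.
- With sex: 0.158 × √(1 − R²), on 37 rather than 38 df. For R² = 0.20 this is 0.158 × 0.894 = 0.141, a fall of 11%.
- Under the fixed quota, the unadjusted variance estimate averages SD²(1 − R²) + (20/19)(δ/2)². This lifts the reported unadjusted SE only slightly, to 0.159 at R² = 0.30, and is ignored below.

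**Type I error and power.** Adjusted power is from the noncentral t with residual SD × √(1 − R²) and 37 df. Unadjusted values are simulated with sex fixed at 10/10. The effect d = 0.8 is an illustrative choice for a more variable outcome.

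| R² | δ for core-temperature change | Fall in SE | Type I error, unadjusted | Power d = 1, unadjusted → adjusted | Power d = 0.8, unadjusted → adjusted |
|---|---|---|---|---|---|
| 0 | 0 | none | 0.050 | 0.869 → 0.868 | 0.693 → 0.693 |
| 1% | 0.10°C | 0.5% | 0.049 | 0.870 → 0.872 | 0.694 → 0.697 |
| 4% | 0.20°C | 2% | 0.046 | 0.873 → 0.882 | 0.696 → 0.710 |
| 10% | 0.32°C | 5% | 0.039 | 0.88 → 0.90 | 0.70 → 0.74 |
| 20% | 0.45°C | 11% | 0.028 | 0.89 → 0.93 | 0.71 → 0.79 |
| 30% | 0.55°C | 16% | 0.019 | 0.91 → 0.96 | 0.72 → 0.84 |

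The adjusted test holds its type I error at about 0.05 throughout.

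**Mixed models.** If a participant random effect is fitted, a sex difference that is constant over time falls in the between-participant variance and does not widen the SE of the age difference in change. Only a sex difference in the change does that, and removing it needs sex × time. A sex main effect alone is not enough.

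**Loss of balance.** The unadjusted age contrast absorbs δ times the difference in the proportion male.
- Metabolic heat production is missing in one young and one older participant. The worst case is 10M/9F against 9M/10F: 10/19 − 9/19 = 1/19, about 5% of δ.
- Purely as illustration, 10M/7F against 7M/10F gives 3/17 of δ. With δ = 2√R² SDs, that is 0.11 SD at R² = 10% and 0.19 SD at 30%.

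**The case against.** The strongest reply is that balance has already done its main job. It keeps sex from confounding age without any model term, and what is left is an efficiency gain of unknown size. The higher shares in the table also require large sex effects: R² of 10% to 30% means 0.32 to 0.55°C, or 63% to 110% of the 0.5°C age effect the study was powered for. At 1% to 4% the gain is between 0.2 and 1.4 power points. The analyses are described in the past tense, so a sex term added now is post hoc. All of this stands, and it limits the point without removing it.

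A reader might infer more than the documents support:
- **That the standard errors are too wide as a matter of fact.** No sex difference or sex-specific SD is given for any outcome.
- **That every outcome differing by sex is affected.** A constant sex difference does not affect a change contrast when a participant effect is fitted.
- **That the loss is greatest for the most variable outcomes.** It depends on sex's share of the variance, not on total variability.
- **That the clothing difference shows a sex effect on the outcomes.** The clothing was chosen to limit clothing effects, and the sex split is the same in both age groups.
- **That missing data have biased the age contrasts.** Imbalance is possible, but apart from metabolic heat production no counts are given here, and no sex split is given for any variable.

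**Conclusion.** The point holds conditionally. Sex was balanced by design, it is available for every participant, and it is omitted without explanation. Where sex affects the quantity tested, the age-group standard error is overstated and the test is conservative. The reduction available runs from about 0.5% to 16% for R² between 1% and 30%, and is zero if sex has no effect. These figures rest on 20 per group, complete 10/10 balance and a common sex effect in the two age groups.

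Under full balance there is no bias and no excess of false positives, so significant age differences stand. The results to read with care are non-significant ones, and those for variables where exclusions may have left unequal sex ratios. The case for acting is the lopsided trade: about 0.001 in power if sex is irrelevant, against a possible gain of 4 to 12 points at d = 0.8 if sex explains 10% to 30%.

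**What to change.** Include sex as a fixed effect in the age comparisons:
- In place of each unpaired t-test, fit a linear model with age group and sex.
- In the mixed models, add sex and sex × time, and state the random-effects structure.
- Report the sex-adjusted age contrast with its 95% CI, and give the number of males and females per age group for each variable with missing data.
- If the analyses have already been run, present the adjusted result beside the unadjusted one and label it post hoc. If sex is to stay out, state why.

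The cost is one sentence in the analysis section and a re-run of existing models: one degree of freedom in the linear model, two terms in the mixed models, and no new data.
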